#### 5.2 Other Clinical Assessments

The following assessment will be evaluated.

• Device performance endpoints peri- and post-procedure:

- Successful vascular access, delivery and deployment of the study valve and successful retrieval of the delivery system
- Grade of aortic valve regurgitation: paravalvular, central and combined
- Device success, defined as absence of procedural mortality, correct positioning of a single transcatheter valve in the proper anatomical location, and intended performance of the study device (indexed effective orifice area [iEOA]
   >0.85 cm^2/m^2 for BMI <30 kg/cm^2 and iEOA >0.70 cm^2/m^2 for BMI ≥30 kg/cm^2 plus either a mean aortic valve gradient <20 mm Hg or a peak velocity < 3m/sec, and no moderate or severe prosthetic valve aortic regurgitation)

- Additional indications of prosthetic aortic valve performance as measured by transthoracic echocardiography and assessed by an independent core laboratory, including EOA, mean and peak aortic gradients, peak aortic velocity, and grade of aortic regurgitation
- Functional status as evaluated by New York Heart Association (NYHA) classification
- Neurological status as determined by the following:
  - National Institutes of Health Stroke Scale (NIHSS) conducted by a neurology professional or certified personnel at discharge and 1 year
  - Modified Rankin Scale (mRS) conducted by a neurology professional or certified personnel at discharge and all follow-up visits
  - Neurological physical exam conducted by a neurologist, neurology fellow, neurology physician assistant, or neurology nurse practitioner in all subjects where stroke is suspected

Health status as evaluated by Kansas City Cardiomyopathy and SF-12 Quality of Life (QOL) questionnaires at baseline, 1 month, 1 year, and 5 years.

For subjects in the CT Imaging Substudy, assessments using 4D CT at 30 days and 1 year will be done as listed below. Data will be evaluated by an independent CT core laboratory.

- Assessment of leaflet mobility
- Assessment of hypoattenuated leaflet thickening (HALT)
- Assessment of leaflet thrombosis

### 5.3 Interim Analyses

Two interim analyses are planned. The administrative interim analysis will be conducted when the first 350 Main Randomized Cohort subjects have completed 1-year follow-up visits. The formal interim analysis will be carried out after enrollment in the Main Randomized Cohort is completed. This formal interim analysis will be conducted on the full N=1500 subjects in the Main Randomized Cohort after the first 1050 subjects in the Main Randomized Cohort have completed 1-year follow-up. The piecewise exponential model based on outcomes among these subjects will be used to estimate the 1-year results

by treatment group for the remaining enrolled subjects. A final analysis on hypothesis of the primary endpoint will be performed on all Main Randomized Cohort subjects with completed 1-year data if non-inferiority cannot be claimed at the formal interim analysis

A Data Monitoring Committee (DMC) will monitor safety events. The DMC reports will be generated according to the DMC charter.

The 4D-CT Cohort (pooling with PMCF 4D-CT subjects) data will be analyzed for the subjects who have completed 30 days, 6 months, and 1-year follow-ups at the time of the formal interim analysis, as appropriate.

For roll-in cohort, data will be analyzed for the subjects who have completed 1 year follow-up and additional data may be provided at the time of the formal interim analysis, as appropriate.

For the ACURATE *Prime* XL Nested Registry cohort, data will be analyzed when all enrolled subjects have completed 30 days follow-up. Additional data may be provided at the time of the formal interim analysis, as appropriate.

Analyses of the Extended Durability Study and the Continued Access Study are not expected to occur at the time when the formal interim analysis is performed on the Main Randomized Cohort. Time of the analyses for the two sub-studies will be based on the data availability.

# 5.4 Subgroup Analyses for the Main Randomized Cohort Subjects

Primary and pre-specified additional endpoints will be summarized for the following subgroups of the Main Randomized Cohort subjects. The subgroup analyses will be performed in the ITT analysis population.

- Age (age <75 years and >=75 years)
- Race and ethnicity (categories with more than 100 enrolled subjects)
- Gender (male and female)
- Valve type (ACURATE neo2, SAPIEN, CoreValve)
- Subject operative risk (extreme/high, intermediate, low)
- Valve size (Small, Medium, Large)

Treatment groups will also be compared in the age, race, and gender subgroup analysis. No adjustments for multiple comparisons will be made. Additional analyses may be performed as appropriate.

In the 4D CT Imaging Substudy, computed tomography data will be analyzed after 200 subjects have reached 1-year follow-up.

# 5.5 Justification of Pooling

### 5.5.1 Pooling Study Centers

An assessment of poolability across sites for the Main Randomized Cohort will be performed. In the analysis, centers with fewer than 5 subjects enrolled in either ACURATE arm or Control arms in the study will not be included in the site poolability analysis using the logistic regression model. Descriptive statistics for the primary endpoint for each individual center will be presented in the report.

Main effects for the study centers and treatment and the interaction of the center by treatment will be included in a logistic regression model with the primary endpoint as the outcome. If the P value for center by treatment interaction is > 0.15, it can be concluded that the treatment effect is not different across the study centers and the data can be pooled across study centers. If the resulting P value is  $\le 0.15$ , the interaction will be examined if it is a quantitative or qualitative interaction, and further exploratory analysis will be performed to identify potential outlier study centers or potential covariates that may explain treatment differences between the centers. The cases from the individual centers will be reviewed and the poolability analysis may be performed by removing the individual centers or by adjusting these covariates. Under this circumstance, descriptive statistics of covariates and the primary endpoint outcomes by treatment group for each site will be provided.

#### 5.6 Multivariable Analyses

Univariate and multivariate analyses will be performed to assess the effect of potential predictors on the primary endpoint and additional endpoints. The following variables will be analyzed as possible predictors:

Category	Covariates		
Treatment	Treatment group (ACURATE=1 vs Control=0)		
Cohort	4D-CT Cohort		
Demographics and Baseline Characteristics	Age at time of consent, Gender, Race, BMI, NYHA, STS Score, EuroSCORE II, Operative risk		
General Medical History	Medically treated diabetes mellitus, History of hyperlipidemia, History of hypertension, History of peripheral vascular disease, Severe Liver Disease/Cirrhosis, History of Dialysis Dependent Renal Failure, History of Chronic Obstructive Pulmonary Disease, Severe lung disease, Severe pulmonary hypertension		
Cardiac History	History of Coronary Artery Disease, History of Myocardial Infarction, History of congestive heart failure, Prior Balloon Aortic Valvuloplasty, Current Anginal Status, History of Percutaneous Coronary Intervention (PCI), History of Coronary Artery bypass Graft (CABG) Surgery, Hostile Chest, Porcelain Aorta, Prior chest radiation therapy, Neuromuscular disease that creates risk for mechanical ventilation or rehabilitation after surgical aortic valve replacement, Orthopedic disease that creates risk for rehabilitation after surgical aortic valve replacement, History of Atrial Fibrillation, History of Atrial Flutter, Prior Pacemaker Implant		
Neurological History	History of cerebrovascular accident (TIA/Stroke), Right Carotid Artery Stenosis (>= 80%), Left Carotid Artery Stenosis (>= 80%), Prior Carotid Endarterectomy / Carotid Artery Stenting		

#### Form/Template 90702621 Rev/Ver AF ACURATE IDE SAP 92400558, Rev/Ver I Page 45 of 64

Frailty	Time to walk 5 meters, Use of wheelchair, Number of falls in the past months, Maximum Grip Strength Average, Katz Basic Activities of Daily Living Score		
Medications	DAPT at baseline (excluding loading dose), Anticoagulant		
Echo Aortic Factors (Core lab)	Aortic valve area AVA (VTI), Mean Aortic valve gradient, Aortic valve peak velocity, LVEF, Transvalvular aortic regurgitation, Doppler Velocity Index (DVI) (VTI), Systolic pulmonary pressure (sPAP)		
CTA (Core Lab)	Annular area, LVOT area		
Peri-procedural Characteristics	Post-dilation balloon performed		
Procedural Characteristics	Total procedure time, Anesthesia type, BAV used during index procedure, Pre-dilation maximum balloon diameter, Total contrast media used for procedure, Total fluoroscopy time, TEE used during the implant procedure, Embolic protection device		

Note: Covariate may not be included in multivariable model due to convergence criterion (GCONV=1E-8) is not satisfied. Covariate may not be included in multivariable model due to missing data on more than 10% of subjects.

Possible predictors will be identified using univariate models with baseline or other identified covariates. These identified predictors from the univariate models with  $p \le 0.20$  will also be modeled multivariately using a stepwise procedure in a logistic regression model. The significance level thresholds for entry and exit of independent variables into the multivariate model will be set at 0.1.

From the final models, predictors will be listed in ascending order of p-value. Univariate analyses will be performed overall as well as separately for each treatment group for the Main Randomized Cohort subjects.

#### 5.7 Other Analyses

The general statistical methods (see Section 4.1) will be applied appropriately for the following analyses. The ITT and implanted analysis sets (see Section 4.2) will be used for following analyses.

### 5.7.1 Baseline Characteristics/Medical History

Baseline data will be summarized to assess subject demographics, clinical history, risk factors, and pre-procedure characteristics.

### 5.7.2 Post-Procedure Endpoints

Post-procedure information will be collected at regularly scheduled follow-up examinations as detailed in the clinical trial schedule in the protocol.

#### 5.7.3 Subject Disposition and Device Disposition

Subject disposition and Device Disposition (e.g., number completing the study, number lost-to-follow-up) will be summarized with frequency tables.

#### Form/Template 90702621 Rev/Ver AF ACURATE IDE SAP 92400558, Rev/Ver I Page 46 of 64

#### 5.7.4 Medication

Antiplatelet and anticoagulant medications will be analyzed at baseline and follow-up visits.

#### 5.7.5 Site reported AE/SAE/UADE

Site reported adverse events will be summarized with frequency tables.

#### 5.7.6 Protocol Deviations

Summary analysis will be provided by protocol deviation categories.

#### 5.7.7 Other Clinical Assessment at various points

- NYHA classification
- 12-lead electrocardiogram (ECG)
- Risk assessments: Society of Thoracic Surgeons (STS) score, euroSCORE II
- Frailty, disability, and comorbidity assessments
- A CT angiogram
- NIH Stroke Scale (NIHSS)
- Modified Rankin Scale (mRS) score
- Quality of Life (QOL)
- SF-12 QOL Questionnaires
- 4D CT at 30 days and 1 year

#### 5.7.8 COVID-19 related analyses

Data collected related to COVID-19 will be assessed. If there is significant impact of COVID-19 on results, additional analyses (eg: sensitivity) will be performed to assess the impact of COVID-19 on the study results according to regulatory guidance.

#### 5.8 Changes to Planned Analyses

Any changes to the planned statistical analyses made prior to performing the analyses will be documented in an amended SAP approved before performing the analyses. Changes from the planned statistical methods after performing the analyses will be documented in the clinical study report along with a reason for the deviation.

#### 6 VALIDATION

All clinical data reports generated per this plan will follow the Global WI: Clinical Data Reporting Validation (PDM 90702587).

### 7 PROGRAMMING CONSIDERATIONS

### 7.1 Statistical Software

Statistical data review will be performed by the sponsor. Statistical analyses will be performed using SAS System software, version 9.2 or later (Copyright © 2000 SAS Institute Inc., [name]. All rights reserved).

### 7.2 Format of Output

Results of analysis will be output programmatically to Word documents from SAS with no manual intervention. All output for the final statistical report will be in the form of a Word document containing tables, figures, graphs, and listings, as appropriate.

### 7.3 Rules and Definitions for Calculated Variables

### 7.3.1 Transthoracic Echocardiographic (TTE) Variables

One transthoracic echocardiographic study will be performed for each visit. If multiple transthoracic echocardiographic studies are performed for the same visit, the latest study performed for each visit will be used for analysis.

7.3.1.1 Body Mass Index (BMI)

Analysis approach: Body Mass Index is calculated for each visit.

Weight (Kg) = Weight (lbs) / 2.20462262. Height (cm) = Height (in) / 0.393700787

$$BMI = \frac{Weight(Kg) \times 10000}{(Height(cm))^2}$$

### 7.3.1.2 Body Surface Area (BSA)

Analysis approach: Body Surface Area (BSA) is calculated using the following formula for each visit if data is available.:

 $BSA(m^2) = \sqrt{(Height(cm)xWeight(Kg))/3600}$ 

7.3.1.3 Indexed Aortic Valve Area (iAVA) or Indexed Effective Orifice Area (iEOA). Effective Orifice Area (EOA) is synonymous with Aortic Valve Area (AVA).

Analysis approach:

Indexed Aortic Valve Area (iAVA) or Indexed Effective Orifice Area (iEOA) is calculated for each visit.

$$iAVA(cm2/m2) = iEOA(cm^2/m2) = AVA(TVI)(cm^2) / BSA(m^2),$$

where AVA (TVI) is the aortic valve area for a specific visit and BSA is the body surface area for the same specific visit under analysis.

#### 7.3.2 Days to Last Follow-up

Valid Data Sources

- Adverse Event Form
- Hospitalization Form
- Procedure Form
- Date of Visit Form
- CEC data
- End of Study

Valid Data Points

- Adverse event dates are "Onset date", "If Hospitalization, is this a new hospitalization, If Yes, admission date", and "If Yes, discharge date" from the Adverse Event Form.
- Admission and Discharge dates are "Admission date" and "Discharge date" from the Hospitalization Form.
- Procedure date is "Date of Procedure" from the Procedure Form.
- Enrollment date is "Date of Enrollment" from the Screening and Additional Informed Consent Form
- Follow-up visit date is "Date of Visit" from the Date of Visit Form at each of the visits (discharge or 7 days post-procedure, 30 days, 6 months, and 1 to 10 years post-procedure).
- CEC event date date of event as adjudicated by the CEC
- End of Study dates of subject withdrawal consent and death.

Last follow-up date will be the latest of the following dates for each subject:

adverse event onset date, admission and discharge dates from hospitalization, procedure date, enrollment date discharge or follow-up visit date, and CEC event date.

If a subject died or withdrawn consent, the date of death or withdrawal (which even came first) should be the last follow-up date.

Follow-up days will be calculated for intent-to-treat analysis set and implanted analysis set

Day 0 is randomization date (ITT) or the procedure date (Implanted)

Days to last follow-up = last follow-up date – randomization date (ITT)/procedure date (Implanted).

Days to (event or last known status) = (event or status) date - randomization date (ITT)/procedure date (Implanted).

#### 7.3.3 Event Rates

The calculation of binary rates will be the same for any endpoint and time point in regard to the appropriate numbers of days as indicated below in Table 1

Table 1. Days Post-procedure to Event and for Adequate Follow-up for ITT and
Implanted Analysis Sets.

Follow-up Visit	Maximum Days to Event	Days for Adequate Follow-up	
	from	from	
	Randomization/Procedure*	Randomization/Procedure**	
30 Days	30	23	
6 Months	180	150	
12 Months	365	335	
2 Years	730	685	
3 Years	1095	1050	
4 Years	1460	1415	
5 Years	1825	1780	
6 Years	2190	2130	
7 Years	2555	2495	
8 Years	2920	2860	
9 Years	3285	3225	
10 Years	3650	3590	

\* Target date for the follow-up visit.

\*\* Start of the follow-up visit window.

Note: For ITT analysis, the Days are from randomization date. For Implanted, the Days are from procedure date (for non-RCT cohorts, the Days are from procedure date).

Binary event rates (proportions) are calculated on a per subject basis.

Event rates through a follow-up visit are calculated using the following for inclusion in the denominator and numerator:

• Denominator:

Subjects in the specific analysis set count in the denominator with one of the following:

- Subject experiences any CEC adjudicated event ≤ maximum number of days as specified in Table 1, as appropriate or
- $\circ$  date of last follow-up  $\geq$  days for adequate follow-up post-procedure from Table 1, as appropriate:
- Numerator:

Subjects in the specific analysis set count in the numerator if the subject experiences specified event  $\leq$  maximum number of days as specified in Table 1, as appropriate.

### 7.3.4 Missing Dates

When calculating rates of adverse events, missing and partial onset dates will be handled as shown in the table below.

Partial Date	Action Taken
Entire adverse event onset date is missing	The procedure date will be used for the onset date.
The month and the day of the month are missing but the year is available	January 1 st will be used for the month and day of the onset date. However, if the imputed date falls before the procedure date, then the procedure date will be used for the onset date.
Day is missing, but the month and year are available	The 1 st will be used as the day of the onset date. However, if the imputed date falls before the procedure date, then the procedure date will be used for the onset date.

For determination of medication history following imputation will be applied for the missing and partial start or stop date of medications.

Medication start or stop date (Partial)	Imputed Date*
Day is missing, but the month and year are available	Consider 1st Day of the month.
Both Day and Month are missing	Consider 1st Day of the month for Day and arbitrarily assign July for the missing month
Year is missing	No imputation

\*If imputed date falls after patient last visit date, then the patient last visit date will be used for the medication last date. The medication start date can be earlier than procedure/randomization dates.

Note: Imputed dates will not be used for "last date" calculation

Form/Template 90702621 Rev/Ver AF ACURATE IDE SAP 92400558, Rev/Ver I Page 51 of 64

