- Device size (Small, Medium, Large, or Extra Large)
- Time of puncture (at site of TAVR sheath) and time of vascular closure for TAVR sheath (introducer insertion and removal time)
- Descriptive information on balloon valvuloplasty (e.g., size of balloon, number of balloon inflations)
- Any devices used and adjunctive procedures performed during the implant procedure
- ACURATE Transfemoral Aortic Valve System catheter insertion and removal time
- Descriptive information on the valve implantation procedure
- Adverse event assessment and associated treatment (including AE, SAE, SADE, UADE, ADE, and CEC events; see Section 19)
- Device deficiencies assessment for the ACURATE Transfemoral Aortic Valve System

Note: All ACURATE transfemoral aortic valve implantation procedures will be performed with the support/presence of trained BSC personnel.

10.8. *Post Index Procedure*

The following are to be performed post-procedure.

- Per society guidelines^{4,5} antiplatelet therapy is recommended to reduce the risk of thrombotic or thromboembolic complications if there are no contraindications to these medications. Subjects must be treated with antiplatelet therapy (aspirin and/or a P2Y₁₂ inhibitor) for at least 1 month following valve implantation. Extended dual antiplatelet therapy may be administered per physician choice. It should be noted, however, that recent clinical evidence points to increased bleeding risk post TAVR among subjects receiving dual antiplatelet therapy or antiplatelet therapy plus anti-coagulation (among subjects indicated for anti-coagulation)^{80,81}.
 - After the valve implant procedure, aspirin (recommended dose of ≥75 mg daily) and/or a P2Y₁₂ inhibitor must be given for at least 1 month. It is recommended that daily aspirin be given indefinitely thereafter as per local standard of care. Aspirin dose may be adjusted to the closest approximation based on local tablet formulation availability. The P2Y₁₂ inhibitor choice and dosing should be per local standard of care.

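### SAP 7.3.4 imputes drug stop dates by the start-date rule with no lower bound, so day-missing stops run about 15 days early and an imputed stop can precede its own start

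*SAP*

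**What the plan says.** The scope sentence in SAP 7.3.4 covers both ends of a course: "For determination of medication history following imputation will be applied for the missing and partial start or stop date of medications". The table below it has three rows.

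- Day missing: "Consider 1st Day of the month".
- Day and month missing: "Consider 1st Day of the month for Day and arbitrarily assign July for the missing month".
- Year missing: "No imputation".

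A footnote supplies the only bound, an upper one: "If imputed date falls after patient last visit date, then the patient last visit date will be used for the medication last date". It adds that a start may precede the procedure or randomization. Nothing ties an imputed stop to the start of the same drug or to a visit record. The adverse-event table in the same section does have a floor: an imputed onset that falls before the procedure is moved up to the procedure date.

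Three other places bear on how the dates might be used. SAP 5.7.4 states that "Antiplatelet and anticoagulant medications will be analyzed at baseline and follow-up visits". SAP 5.6 lists "DAPT at baseline (excluding loading dose), Anticoagulant" among the candidate predictors. Protocol 10.8 (Post Index Procedure) requires antiplatelet treatment "for at least 1 month following valve implantation". Protocol Table 10.1-1 collects antiplatelet and anticoagulant drugs at screening, at the procedure, at discharge and at every follow-up contact.

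**The concern.** The first of the month is a natural early choice for a start date. For a stop date it is the earliest date consistent with the record, so it can only shorten the course when the start is known. With no floor, it can also give an interval that cannot exist.

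An example shows the effect. A subject is implanted on 15 May and stops a P2Y12 inhibitor on 20 June, recorded only as June. The true course is 36 days; the imputed stop of 1 June makes it 17. At day 30 (14 June) the subject was on the drug, but the imputed dates say off.

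What is at stake is on/off status in the medication summaries, mainly at the 30-day visit, which lies next to the protocol's one-month minimum. To a lesser degree it is the coding of the medication covariates in SAP 5.6.

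**Working it through.** The documents give no figure here, so there is nothing to reproduce. I applied the written rule to each day of a 365-day year. Assumptions: true dates evenly spread over the year, fixed course lengths, and the last-visit cap not reached. Shift means imputed stop minus true stop.

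**Day-missing stop.** In a month of m days the shifts sum to −m(m−1)/2.
- Seven 31-day months: 7 × 465 = 3,255. Four 30-day months: 4 × 435 = 1,740. February: 378. Total 5,373.
- Mean shift: −5,373/365 = −14.7 days, range −30 to 0. It is zero only when the true day is the 1st (12/365 = 3%), so 97% of dates move earlier.

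**Day-missing stop, start known: stop before start.** This happens when a course of L days begins after the 1st and ends in the same month, which is m − L − 1 start days per month.
- L = 7: 7×23 + 4×22 + 20 = 269; 269/365 = 74%.
- L = 14: 7×16 + 4×15 + 13 = 185; 185/365 = 51%.
- L = 30 or more: none. But a true 30-day course averages 30 − 14.7 = 15.3 days.

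**Year-only stop (1 July is day 182; the mean day is 183).**
- Mean shift: 182 − 183 = −1 day, range −183 to +181. It is early for 183/365 = 50.1% of dates and late for 181/365 = 49.6%.
- Stop before start, start known: the course begins after 1 July and ends in the same year, so (183 − L)/365. L = 30: 153/365 = 42%. L = 90: 93/365 = 25.5%. L = 180: 3/365 = 0.8%. For example, a start on 10 September with a year-only stop gives −71 days.

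**Both dates missing only the day.** The two shifts cancel on average (a 30-day course averages 30.0 days) and no interval is negative, though 77% of 7-day courses collapse to 0 days.

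**Status at day 30, if derived from dates.** I crossed all 365 implant days with equally likely true stops. For day-missing stops that truly fell 31–60 days after implant, 46% are imputed to before day 30, so the subject appears off drug. For true stops at 31–90 days the share is 23%.

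**Alternatives.** The mean true day of the month is 1 + 14.72 = 15.72. Imputing the 15th gives a mean shift of 15 − 15.72 = −0.7 day, range −16 to +14. Imputing 31 December for year-only stops gives 365 − 183 = +182 days on average before the cap.

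**The case against.** The best defence is that little depends on these dates. No exposure-duration or one-month compliance analysis is defined; SAP 5.7.4 summarises use by visit. Visit records hold the same information, and the SAP does not say whether status comes from them or from start and stop dates. SAP 7.3.4 keeps imputed dates out of the last-follow-up calculation. The SAP's revision history describes the missing-date rules as having no effect on the primary endpoint analysis. The rule is the same in both arms. All of this stands, and it limits the reach of the point.

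A reader might infer that the rule shortens antithrombotic exposure throughout. The text does not support that. The 1 July value is late about as often as early, and day-missing starts move early too, which offsets the stop shift when both days are missing. A reader might also infer that compliant subjects would be reported as early stoppers. The requirement is for aspirin and/or a P2Y12 inhibitor, with aspirin recommended indefinitely, so a shortened P2Y12 course alone does not make a subject non-compliant. Nor does a post-implant stop date usually bear on a baseline covariate; it matters there only if the imputed stop lands before baseline. The model is in any case a stepwise predictor screen.

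The defence does not answer the missing floor. A rule that lets a drug end before it begins is wrong as written, however often it applies.

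**Conclusion.** The point holds in a limited form. Day-missing stops are biased early by about 15 days (at most 30), which shortens a course when its start is known. Both day-missing and year-only stops can fall before the drug's start or before a visit recording it as current. The likely consequence is misclassified on/off status near visits, chiefly at 30 days, and possibly some error in medication covariates. The year-only rule adds noise and impossible intervals, not a systematic shortening.

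The percentages rest on evenly spread dates, an inactive last-visit cap and, except where stated, a known start. They apply only to records with partial dates. The documents do not say how many there will be, so the overall effect cannot be sized. The day-30 shares further assume that status is derived from dates.

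**What to change.** In SAP 7.3.4, separate stop dates from start dates:

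- Floor every imputed stop at the start date of the same medication record and at the last visit at which that drug was recorded as current. Keep the cap at the last visit date.
- For day-missing stops, use a value that is not always early, such as mid-month, under the same floor and cap.
- For year-only stops, keep 1 July with the floor and cap. Do not move to 31 December, which would replace a mean error near −1 day with about +182 days before the cap.
- Leave the first-of-month rule for start dates.

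Both parts are needed: the floor removes impossible intervals but does not by itself remove the 15-day shift. The cost is SAP wording and one extra programming rule on data already collected. Some imputation error will remain in short courses, since a mid-month value can be about two weeks off in either direction.
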